After recruits have passed the initial screen, first they will pass a verification check for their phone, email and webcam, or they will not be eligible to participate. Next, each recruit will complete a second screening survey to confirm eligibility in case of long lapse of time. In addition we will contact them via webcam to verify their identities and confirm their interest in participation. This will be a trial run for the remote collection of salivary cotinine test pictures for bioconfirmation of abstinence that will occur at 3 and 6 months that will take place via webcam with photo IDs.

The screening survey will assess demographic variables that will be used for dyad formation. After the randomization to study condition, the 20 smokers in each treatment group will be coupled into 10 demographically homophilous dyads or buddy pairs based on certain screening data. To determine the specific variables to use to form homophilous dyads, we will rely on analyses that are underway that correlate similar demographics with tie strength in our prior Tweet2Quit groups.

Standard Resources given to Participants (Initial and Main Study Groups)

All participants, regardless of assignment, will receive an integrated smoking cessation plan to ensure an equitable and adequate intervention dose for all participants. The integrated plan, including free nicotine patches and gum/lozenges, referral to the NCI Smokefree.gov Quit Guide and encouragement to set a quit date, represents a standard intervention for people desiring to quit smoking. The purpose of our study is to examine the potential efficacy of including Twitter-enabled interactive peer texting as a low-cost, accessible added intervention to the standard protocol. Participants assigned to control will not be prevented from following the very large existing Twitter quit smoking groups that are publically available on Twitter; but they will not be assigned to small, private quit-smoking groups with computer-generated feedback, like the treatment groups will be. Our proposed intervention is consistent with U.S. Clinical Practice Guidelines, which recommends nicotine-replacement therapy and the setting of a quit date, consistent with our protocol.

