All participants (Twitter Coed, Twitter Women only, and control) in both phases will be given an integrated treatment for smoking cessation, via the website that we develop. The website will provide access to an evidence-based set of "base" treatment materials in one central location, that all participants will be encouraged to use. The website will have a section on proper use of the free nicotine patches and gum/lozenges that will be provided, and it will remind participants about their quit date. Throughout the study, treatment and control participants will be emailed links to numerous different SmokeFree.gov modules and embedded codes in the emails will allow us to track which modules they view and what other resources they use.

All participants will be offered 8 weeks of free nicotine patches and 8 weeks of free nicotine gum or lozenges, but will not be required to use the patches or gum/lozenges. Each participant will be mailed 8 weeks of nicotine patches and 8 weeks of nicotine gum or lozenges at the recommended dosages (with tapering) and with usage instructions with the similar instructions available on the website. However,

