After each treatment group ends, if a participant needs more support they can join a group created on Facebook by Tweet2Quit to participate with group members from all treatment groups. Treatment participants have to request to enter the Facebook group and research personnel will accept participants in the group and similar kick members if needed. The participants are free to talk to each other, but there will be no intervention. Approximately once per week we will be posting current quit smoking information to the group. There will be no direct contact to any particular individual in the group. Messages sent via this group will not be collected or analyzed.

Collaborations with Other Campuses

Although UCI is collaborating with UCSF, Investigator [name] is not engaged in human-subjects research, given he is not interacting with participants, and he is not accessing identifiable data. UC Reliance #977 is *inactive*

UCI will be working with personnel from both UCSF and Stanford University in the analysis portion of this study. Survey and Abstinence results will be shared with the other sites. UCI personnel will remove all identifiable data from the files prior to sharing with the other sites. Data will be shared via encrypted Excel files that only the authorized personnel will have the password to. [name] has secured IRB approval with Stanford University and will be working in collaboration with UCI. No subject enrollment or data collection will be conducted at Stanford. Data will be shared between Stanford and UCI primarily in a de-identifiable fashion but some datasets may include minimal identifiable data (Twitter usernames). [name] will also receive subject-identifiable data from UCI in the event of a serious adverse event, but will not receive identifiable data at any other time. In sum, both de-identifiable data and identifiable data will be seen by [name] while working from Stanford. [name] will be conducting his portion of the study from UCSF, however he will not have access to identifiable data. Both of these

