researchers will be involved in the analysis portion of the data collected during this study. [name] will also be assisting in randomizing the groups but he will only use de-identified subject IDs for randomization and data analysis. [name] will have no interaction with human subjects. [name] has moved from her postdoc position at Stanford to an assistant professor position at Michigan State University. She will be involved with supplemental data analysis related to our exploratory goals and will only see de-identified data. She will not be involved with subject enrollment, data collection, primary data analysis or adverse events monitoring. [name] will not have access to subject indefinable data nor will she be interacting with human subjects.

All data will be sent as a password encrypted Excel files via email. Only personnel listed in this protocol will receive these files, as well as the password. UCI is the coordinating site for this research project. The PI ([name]) as well as the Project Coordinator and Research Assistants that are running the study will be working out of the UCI campus. UCI campus is the coordinating site as a result of the location of employment for the previously mentioned personnel. UCSF and Stanford University will be working in concordance with the UCI campus and staff electronically to assist in conducting the study and analyzing the data.

2. Off-Site Research –

- a. See [Guidance for Letter\(s\) of Permission](#)
- b. See [Template Letter of Permission](#)

Check here to confirm [Letter\(s\) of Permission](#) has been / will be obtained and kept on file.

B. Measures / Data Sources

1. List the measures that will be administered or data sources that will be accessed.
2. Submit **data collection instruments** (e.g., data abstraction sheet listing the variables that will be collected/analyzed for records reviews, measures, questionnaires, list of interview or focus group questions, observational tool, etc.).

Data Collection and Measures

Surveys will be sent out at 1, 3 and 6 months post-quit date to assess abstinence (see measures below). Additional questions will ask about their use of nicotine patches and gum/lozenges, NCI's Smokefree.gov Quit Guide, as well as anything else they used to help quit smoking. They will also be asked their use of Tweet2Quit if they are in the treatment condition (both Coed and Women-Only groups).

Primary Outcome Measure:

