Upon enrollment, each participant will be assigned a unique ID code and these codes will be used on the surveys; i.e., participants' names will not appear on the surveys. All data collection and entry will be automated using web-based surveys (Qualtrics), and the data will be stored on secure servers and secure personal computers accessible only to research personnel using personal login names and passwords. No data will be stored on portable memory devices. The identifiable data will be maintained and destroyed consistent with university data storage policies, typically six years after completion of grant funding or after confirmation that all data analyses have been completed.

Facebook Alumni Group

With the inclusion of an alumni group for all treatment participants to join at the end of each group, participants will use their personal accounts. Since each participant uses their own account, we can't restrict participants access each other's profiles. Facebook does supply privacy settings so that participants can restrict other participants from accessing their profile or if their profile is set to public then it is normally available to all users. As Tweet2Quit is the moderator for the group, only verified members can join and researchers have the ability to remove participants if a participant misbehaves so risk is minimal.

C. Potential Benefits

Discuss the potential benefits directly **to the participant and to society**. **Compensation (i.e., gift cards, cash, course credit, etc.) is not a benefit.**

There is no direct benefit anticipated for the participant.

OR

The main direct benefit is that all participants will receive access to smoking cessation and relapse prevention information, a beneficial cessation protocol, and NRT which should help them to quit smoking or at least reduce their smoking. Providing 8 weeks of nicotine patches at no cost to participants should be a strong incentive to maintain cessation at least for those 8 weeks (as well as 8 weeks' worth of nicotine gum/lozenges to use throughout that time). People who try to quit smoking but fail have a better chance of quitting next time around. Thus many participants should eventually experience direct health benefits. In addition, we expect the Tweet2Quit treatment protocol to further increase cessation rates for those participants.

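### Does the pooled Facebook alumni group undermine the women-only versus coed comparison at 6 months?

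*Protocol*

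**What the plan says.** The Protocol sets the Twitter treatment at 3 months within a 6-month study (Section 6A, Main Phase). The primary outcome is sustained, cotinine-confirmed abstinence at 6 months after the quit date (Section 6B). Aim 2 compares 240 women in women-only groups with 240 women in coed groups (Section 1).

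On the alumni group, Section 6A says that treated participants who need more support after their group ends may enter, and "they can join a group created on Facebook by Tweet2Quit to participate with group members from all treatment groups". Entry is controlled: "Treatment participants have to request to enter the Facebook group and research personnel will accept participants in the group". Staff post quit-smoking information about weekly, and the section says there is no intervention. It adds: "Messages sent via this group will not be collected or analyzed". Section 7B repeats the pooling: "With the inclusion of an alumni group for all treatment participants to join at the end of each group".

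The follow-up surveys (Section 6B, Data Collection and Measures) ask about the aids supplied, "as well as anything else they used to help quit smoking". For treated participants, "They will also be asked their use of Tweet2Quit if they are in the treatment condition". The survey forms are not in the documents.

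For controls, no alumni access is described. They do receive quitting information: "Throughout the study, treatment and control participants will be emailed links to numerous different SmokeFree.gov modules". They may also find peers elsewhere: "Participants assigned to control will not be prevented from following the very large existing Twitter quit smoking groups" (both Section 6A, Standard Resources).

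The SAP compares women by the arm to which they were randomised and does not mention the alumni group.

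**The concern.** Group composition is the only thing Aim 2 varies, and the alumni group removes that separation halfway to the endpoint. If being among women only helps women stay abstinent in months 3 to 6, contact with coed graduates could erode the benefit and pull the 6-month difference towards zero. With no described record of who joined or when, a reader of a null Aim 2 result could not tell an absent effect from a diluted one.

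For Aim 1 the worry is different. Optional peer contact in a study-run group is available to 480 coed participants and, as far as the documents say, to none of the 240 controls. The 6-month difference then reflects Tweet2Quit plus that access, which the SAP does not spell out.

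**Working it through.** **1. Who is exposed, and when.** Treatment ends at month 3 and the endpoint is at month 6, so access overlaps 6 − 3 = 3 months. Eligible participants number 480 + 240 = 720. Access is the same for every treated participant, so it does not differ between the two Aim 2 arms.

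**2. Whose outcome can change.** The primary outcome runs from the quit date and allows at most five instances of use. A woman already past that limit at month 3 has failed whatever happens later. Mixing can act only on women still abstinent at month 3.

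**3. Scale.** The documents state no alpha, power, abstinence rate, intracluster correlation or uptake, so there is no figure to reproduce. Everything below is an assumption, used only to show scale.

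With 240 per arm, 15% in coed, two-sided 5%, unpooled variance and no clustering, the women-only rate giving 80% power is 25.16%:

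- SE = √[(0.15×0.85 + 0.2516×0.7484)/240] = 0.0363
- 0.1016/0.0363 = 2.80, and Φ(2.80 − 1.96) = 80%

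Loss = a × u × d × f, where:

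- d is the women-only retention advantage from month 3 to month 6, over an assumed 60% in coed;
- a = 25.16%/(0.60 + d) is women-only abstinence at month 3;
- u is uptake among abstinent women;
- f is the share of the advantage that joiners lose.

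With d = 0.10, a = 25.16%/0.70 = 35.9%.

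| u | f | Loss (points) | Power |
|---|---|---|---|
| 0 | any | 0 | 80% |
| 5% | 1 | 0.18 | 79% |
| 10% | 0.5 | 0.18 | 79% |
| 10% | 1 | 0.36 | 77% |
| 30% | 0.5 | 0.54 | 76% |
| 30% | 1 | 1.08 | 71% |

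With d = 0 the loss is zero at any uptake.

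A harsher model lets joiners in both arms move to the average of the two retention rates. Assume 30% (coed) and 37% (women-only) abstinent at month 3, with retention of 66.7% and 81.1%, average 73.9%. The 6-month rates without mixing are 20% and 30%. If 25% join:

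- coed: 0.30 × (0.75×0.667 + 0.25×0.739) = 20.6%
- women-only: 0.37 × (0.75×0.811 + 0.25×0.739) = 29.3%

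The difference falls from 10.0 to 8.8 points, and power (pooled variance under the null, no clustering) from 71.7% to 60.5%. The result depends on uptake and retention, neither of which the documents give.

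**4. What a split would do.** Treatment groups have 20 members (Section 6A, Enrollment Process and TweetStreak). That makes 240/20 = 12 women-only and 480/20 = 24 coed groups, so separate alumni pools would draw on numbers in a 1:2 ratio. At 10% to 30% joining, one women-only group supplies 2 to 6 members. Equal access would become arm-dependent support.

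**The case for a change.** The strongest case for acting is that the group is created, moderated and supplied with posts by the study. Calling it no intervention does not remove peer contact, which is the mechanism under test. Tweets are captured nightly, whereas nothing in the documents says that joining is recorded. Logging a date at approval would cost almost nothing, and the SAP could define the estimand in a sentence or two. The limit in step 2 also does not protect 7-day point prevalence at 6 months, where women who relapsed earlier can still be influenced.

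The facts in this stand: the pooling is real, the timing is before the endpoint, and the SAP is silent. The inference to a needed change does not. The SAP's Aim 2 question concerns the group type to which a woman is randomised, and that treatment lasts three months. Whether its effect persists under common later access is a coherent question, and the planned analysis answers it. Keeping the formats apart to month 6 would ask a different one.

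The alumni group is also aimed at people who want more help, some of whom may already have relapsed, so uptake among abstinent women could be low. Staff approve every request and admit only verified members, so a count of joiners may be recoverable, and the surveys may pick up some use. Joining happens after randomisation, so even a perfect log would support only description.

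**Conclusion.** No change is needed. Comparison by assignment remains valid in both aims, for Tweet2Quit in the assigned format followed by optional alumni access. That access is equal across the Aim 2 arms and, for Aim 1, part of what treated participants are offered.

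Dilution of the 6-month Aim 2 difference is possible but of unknown size. It is zero if nobody joins or if composition no longer matters after month 3. In the first model it is 0.2 to 0.4 points at 10% uptake and 0.5 to 1.1 points at 30%; the harsher model loses 1.2 points at 25%. All of these rest on assumed rates, uptake and retention, and ignore clustering.

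The natural check is already planned: sustained abstinence at 3 months is a secondary outcome for both aims and almost wholly precedes alumni access. Setting it beside the 6-month result shows whether a difference present at treatment end later faded, though not why. Splitting the group is a trade-off with costs of its own: unequal pools, two access regimes within one trial, and a contrast extended past treatment. Counting joiners by arm and describing the package in the trial report is sensible practice that analysts can follow without altering any planned test or estimate.

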In addition, participants will complete a contact form which will ask for their name, mobile phone, home and/or work phone if applicable, home mailing address (to get the nicotine patches and nicotine gum/lozenges), email address (to get survey links), Facebook URL or Social Media picture (to validate they have a social media account), identifying photo (to post on Tweet2Quit Twitter account if applicable and to verify identity for saliva testing), and username and password for our website (and Twitter if applicable). In addition, they will be asked to supply additional names, phone numbers, and email addresses of collaterals which will only be used as last resorts to contact the participants. If the participant fails to provide the required personal information, s/he will be disqualified. Also an automated program will send both an email and a text to each participant and require a response to ensure both accounts are valid. If a participant fails, their photo will not be downloaded from the survey database. Those that pass will have their photographs used to verify identity during webcam interviews (for saliva tests). If the

participant is enrolled into a Twitter group, their photo will be used for their profile picture. After the study concludes, all copies of the pictures will be destroyed.

The screening survey will also ask about age, gender, marital status, years of education, race/ethnicity, employment status, years smoking, cigarettes per day, number of prior quit attempts, age when they started smoking, type of cigarettes they used, the Fagerstrom Test for Nicotine Dependence (FTND), and the Thoughts about Abstinence Scale^{103,104}. It will also assess use of other tobacco and ENDS (electronic nicotine delivery) products. It will assess social media use, and self-monitoring and self-disclosure as personality traits. The screening survey will also explain the study requirements to participants (e.g., the study may involve tweeting and receiving text messages on mobile phones daily, will involve taking surveys, etc.) and it will confirm that the participant understands and agrees to these study requirements.

If participants fail the screen, they will be thanked and referred to NCI's Smokefree.gov Quit Guide. No more communication will occur and they will be blocked to prevent re-attempts at enrolling. Their data will be kept for screening analyses, but not used as part of the study results.

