Percentage of participants with 7-day point prevalence abstinence at 6 months. Percentage of participants who reported no use of tobacco products by answering the questions: 'How many cigarettes have you smoked', 'How many other tobacco products have you used', and 'How many times did you use an e-cig' over the past 7 days (assessed at 6 months post quit date) confirmed by salivary cotinine measurement (assessed at 6 months post quit date).

At 3 and 6 months post-quit date, those that report as abstinent will have their abstinence confirmed using salivary cotinine Alere iScreen OFD test kit. Participants will be sent a test kit in the mail and then contacted via webcam to show their photo ID and perform the test on camera, then a picture will be taken and then texted back to UCI. The pictures will consist of the saliva kit placed on top of the paper they receive which has their appointment time and their name. The picture will be stored in a secure database via the internet. The kits results will read either pass (a salivary cotinine level 0-30ng/mL) or fail (>30ng/mL). Web-based video recordings to verify smoking status have been successfully employed in Internet smoking cessation research; mailed saliva cotinine test kits have been successfully used; and this has been done in [name] trial with young adult smokers (UCSF IRB #11-06294). During the study, video and audio conferences with the participants will not be recorded. The consent form will indicate that participants may be requested to provide a saliva test and will be provided a small incentive (\$40 gift card per test) for completing it. In practice, only those who report being abstinent will be sent the cotinine test. If the participant's webcam and/or camera on their phone breaks during the course of the study, they have the additional option of mailing their kit. Kits collected this way will have a picture taken of the results, then the kit will be properly disposed.

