Saliva tests will be provided to participants to get accurate responses for abstinence. The test is a non-obtrusive collection of a biological specimen. There are no side effects to using the kit. Instructions will be provided to avoid this problem and administration will be overseen by research personnel via webcam to ensure safety. Alere iScreen OFD is available over the counter and considered safe for the population. Proper instructions will be given with the kit, in an email, and via webcam conference with the UCI research personnel. A picture of the test kit will be electronically sent to research personnel after completion of the test. After the pictures are returned to UCI, abstinence will be recorded and identifiers removed. Other research personnel will only have access to the unidentified results. After the saliva test is completed, the kit will be discarded by the participant. Video and audio will not be recorded during the webcam conferences. If the participant's webcam and/or camera on their phone breaks during the course of the study, they have the additional option of mailing their kit. Kits collected this way will have a picture taken of the results, then the kit will be properly disposed.

[X] This study involves the collection of participant identifiable data (even if temporary such as for recruitment or compensation purposes), and as such, a breach of confidentiality is a risk associated with the research.

2. Discuss what steps have been taken and/or will be taken **minimize and prevent** any risks/potential discomforts described above.

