This study includes **children**. Identifiable information/biospecimens will be retained for seven years after all children enrolled in the study reach the age of majority [age 18 in California].

This research involves **Protected Health Information (PHI)**. Identifiable consent/assent forms and HIPAA forms, as applicable, will be retained for six years after study closure. *Investigators must destroy PHI at the earliest opportunity, consistent with the conduct of this study, unless there is an appropriate justification for retaining the identifiers or as required by law.*

Identifiable information/biospecimens will be destroyed once research data is analyzed and/or after publication/presentation.

Other; specify time frame and provide the rationale: <Type here>

D. Photographs, Audio/Video Recordings Retention

1. If subject identifiable audio or video recordings will be collected, specify the timeframe for the transcription and describe retention/destruction plans.

Not applicable: Identifiable audio/video recordings will not be collected.

Audio or video recordings transcribed; specify time frame: <Type here>

Audio or video recordings will be maintained; specify time frame: <Type here>

Audio or video recordings maintained indefinitely; provide the rationale: <Type here>

Audio or video recordings destroyed; specify time frame: <Type here>

2. If subject identifiable photographs will be collected, describe retention/destruction plans.

Not applicable: Subject identifiable photographs will not be collected.

Photographs will be maintained; specify time frame: <Type here>

Photographs maintained indefinitely; provide the rationale: *Photographs of completed saliva test will be kept indefinitely to reconfirm biocomfirmation if needed. Photographs of participants will be deleted after group closure.*

Photographs destroyed; specify time frame: <Type here>

E. Certificate of Confidentiality

1. Indicate whether a Certificate of Confidentiality (CoC) has been or will be requested.

Not applicable: No CoC has been requested for this study.

This is a non-NIH funded/supported study. Choose one of the following:

A CoC will be requested for this study. *The CoC application must be submitted to the IRB staff for review after IRB approval.*

A CoC has been obtained for this study. *Provide a copy of the CoC Approval Letter.* The expiration date of this CoC is: <Type here>

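### When the webcam fails, a saliva kit can be mailed with no stated identity check or observation, and the primary outcome does not separate such a pass from a witnessed one

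*Protocol*

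**What the plan says.** The normal procedure is in Protocol Section 6.B (Data Collection and Measures). Those who report abstinence at 3 or 6 months receive a kit and are "contacted via webcam to show their photo ID and perform the test on camera". A picture of the kit, lying on a sheet with the participant's name and appointment time, is then texted to the study office. Under Section 6.A (Enrollment Process), recruits are told that "first they will pass a verification check for their phone, email and webcam, or they will not be eligible to participate", and an enrolment photo is held to verify identity at the saliva tests.

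The exception is in the same part of Section 6.B: should the webcam, the phone's camera or both fail after entry, "they have the additional option of mailing their kit". The only handling described is: "Kits collected this way will have a picture taken of the results, then the kit will be properly disposed". Section 7.B (Alere iScreen OFD – Saliva Test Kit) repeats both sentences, and also says that "administration will be overseen by research personnel via webcam to ensure safety".

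The primary outcome in Section 6.B requires salivary cotinine confirmation at 3 and 6 months, with no condition on how the sample was collected. The SAP (Statistical Analyses) likewise refers only to biochemical salivary cotinine verification.

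On the photos, Section 6.A says: "After the study concludes, all copies of the pictures will be destroyed". Section 10.D says: "Photographs of participants will be deleted after group closure".

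**The concern.** Testing 6-month efficacy with biochemical verification is the stated purpose of Aim 1, and the protocol calls its primary coding the most rigorous one. Verification has that force only if the saliva is known to be the participant's. The webcam route secures this through photo ID and live observation. When the webcam has failed, the mailed route as described does neither, and a negative strip then shows only that somebody's saliva was negative.

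Participants know their arm, and Section 7.B accepts that some may be embarrassed if they do not quit. Twitter members report to a peer group and controls do not, so the pressure to appear abstinent may differ between the Aim 1 arms. This is plausible but not shown. In Aim 2 both groups are Twitter groups, so the argument is weaker there.

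As written, the analyst would not know which passes were unwitnessed and could not test whether they matter.

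**Working it through.** **Step 1: the two routes side by side**

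| Control | Webcam route | Mailed route |
|---|---|---|
| Photo ID at the test | yes | none stated |
| Test watched live | yes | none stated if the webcam failed |
| Picture of the result | yes, with name and appointment time | yes; labelling not stated |
| Proof of the equipment fault | not applicable | none stated |
| Collection mode recorded | not stated | not stated |

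The trigger covers two different faults. If only the phone camera fails, the test can still be watched by webcam, and mailing merely replaces the texted picture. If the webcam fails, observation is lost. The text does not separate the two cases.

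**Step 2: does anything downgrade a mailed pass?** The primary analysis has one test-based rule: a positive result from any source is nonabstinent. Nothing covers an unwitnessed negative. The additional analyses in Section 6.B concern nicotine replacement and ENDS use. The SAP's sensitivity analyses concern missing data (missing counted as smoking; respondents only). None uses collection mode. Since mailing sits inside the confirmation procedure and nothing excludes it, the natural reading is that a mailed pass counts. This is an inference; the documents do not say so.

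**Step 3: scale.** There is no figure in the plan to reproduce. From the documents: control n = 240, coed Tweet2Quit n = 480 (Section 1, Aim 1). Assumed: true rates, two-sided 5% level, misuse rates. Clustering is ignored, so these are not estimates of the trial's power.

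*Effect on the estimate.* Assume true rates of 25% vs 15%, and 15% of each arm falsely claiming abstinence.
- 10% of false claimers in each arm pass with another person's mailed sample: 15% × 10% = 1.5 points per arm. The ratio goes from 25/15 = 1.67 to 26.5/16.5 = 1.61; the 10-point difference is unchanged.
- 5% in each arm: 15% × 5% = 0.75 point.
- 15% in the coed arm and 5% in control: 2.25 − 0.75 = 1.5 points of spurious difference.

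*Effect on the test.* Let f be the share of true non-abstainers finally counted as abstinent through unwitnessed kits. The observed rate is p + (1 − p)f. Power is Φ[(d − 1.96·SE₀)/SE₁], where d is the observed difference, SE₀ the pooled and SE₁ the unpooled standard error. Example, 10% vs 20% with f = 2% in both arms: control 0.10 + 0.90 × 0.02 = 0.118; coed 0.20 + 0.80 × 0.02 = 0.216; d = 0.098; SE₀ = 0.0306; SE₁ = 0.0280; power 91.3%.

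| Equal f in both arms | 0% | 1% | 2% | 5% |
|---|---|---|---|---|
| True 10% vs 20%: ratio | 2.00 | 1.91 | 1.83 | 1.66 |
| Power | 94.4% | 92.9% | 91.3% | 85.8% |
| True 20% vs 30%: ratio | 1.50 | 1.48 | 1.45 | 1.40 |
| Power | 82.8% | 81.3% | 79.8% | 75.2% |

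For the false-positive risk, assume no true effect and f in the coed arm only. The rejection probability adds both tails; false passes are (1 − p) × f × 480.

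| f in the coed arm only | 0% | 1% | 2% | 5% |
|---|---|---|---|---|
| Base 10%: false passes | 0 | 4.3 | 8.6 | 21.6 |
| Rejection rate | 5% | 6.3% | 10.5% | 38.9% |
| Base 20%: false passes | 0 | 3.8 | 7.7 | 19.2 |
| Rejection rate | 5% | 5.6% | 7.6% | 22.2% |

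**Step 4: the photo dates.** Group closure is not defined. The Twitter treatment lasts 3 months of a 6-month study. If closure means the end of the Twitter group, the reference photo is gone before the 6-month test. If it means the end of the cohort's follow-up, it is not.

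**The case against.** The strongest reply is that this is a narrow exception for equipment that fails after entry. A webcam check is an eligibility condition, only self-reported abstainers are tested, and the option is open in every arm. The primary outcome needs confirmation at both 3 and 6 months, so a participant who smoked throughout would have to get past two tests as well as under-report on the surveys. All of this stands and keeps the likely number small. One limit: someone who relapsed after a genuine 3-month pass would need only one false pass.

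Several stronger readings are tempting, but the documents do not support them.

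- A reader might infer that nobody watches any mailed test. After a phone-camera failure alone, the webcam session can still take place.
- A reader might infer that the route serves precisely those who would fail on camera. It is open to anyone whose camera breaks.
- A reader might see the $40 as a motive. It is paid for completing the test, so a participant who fails on camera receives it too.
- A reader might suspect that postal transit alters the strip. Nothing in the documents shows this.
- A reader might conclude that identity checking is lost at 6 months because the enrolment photo has been deleted. That depends on what group closure means, and the webcam route still requires photo ID at the test.

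Finally, scoring every mailed kit as unconfirmed in the primary analysis would misclassify genuine abstainers whose equipment failed. That is a fair argument against imposing it as the only coding. It does not argue against recording the route and testing its influence.

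**Conclusion.** The point holds as a gap in verification and analysis: an unwitnessed, unidentified pass can confirm abstinence in the primary outcome, and neither its coding nor its influence is addressed. It does not show that the primary result would be biased. The number of mailed kits is unknown and probably small. Equal misuse mainly dilutes the relative effect; in the example with 10% vs 20%, f = 1% to 2% costs about 1.5 to 3 points of power. A false effect requires misuse to differ between arms, and the larger rejection rates at f = 5% need about 19 to 22 successful false passes, all in the coed arm. Every misuse rate and abstinence rate here is assumed. The conclusion also rests on the inference that mailed passes count. This is a cheap improvement worth making, not a fatal flaw. The conflict over photo deletion is real but secondary.

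**What to change.** 1. In Sections 6.B and 7.B, state that a participant with a failed camera is first offered a webcam session on another device. If only the phone camera has failed, keep webcam observation with photo ID and use mailing only to replace the texted picture. This also reconciles the oversight statement in Section 7.B with the mailing option beside it.
2. Record the collection mode of every test (witnessed with ID, or unwitnessed) and report the counts by arm and time point.
3. State in the outcome definition and the SAP how unwitnessed passes are coded in the primary analysis. Pre-specify a sensitivity analysis of both primary aims that codes them as not bioconfirmed. Making that the primary coding, with the reverse as the sensitivity analysis, is equally acceptable if stated in advance.
4. Reconcile Sections 6.A and 10.D so that the reference photo is kept until the cohort's last 6-month saliva test. Tie this to the test and not to a calendar date, because Section 9 allows 6-month tests to be pursued for more than 3 months after the participant qualifies.

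The cost is one extra data field, a few sentences and one additional analysis per aim, with no new study visits. Some genuine abstainers will count as unconfirmed wherever the stricter coding is used.
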